## **9. FINAL SUBJECT STATUS**

A study termination form will be completed for each study subject who receives study product. This includes subjects who completed the study or who withdrew or were withdrawn from study.

### **9.1 COMPLETED, DISCONTINUED OR INCOMPLETE SUBJECTS**

A completed subject is a subject who has satisfied all study entry criteria and completed the 52-week study. For any subject who has started study and terminates the study prematurely, every effort will be made to obtain final evaluations of clinical status. Reasonable effort will be made to contact any subject lost to follow-up during the course of the study in order to complete assessments and retrieve any outstanding data and clinical supplies. The investigator will choose the description that best describes the status of the subject at termination.

1. Subject completed the 52-week study period

OR INCOMPLETE/DISCONTINUED DUE TO:

2. Contact dermatitis
3. Adverse experience
4. Serious adverse experience
5. Pregnancy
6. Protocol violation
7. Subject withdrew consent
8. Subject lost to follow-up
9. Other

## **10. STUDY PRODUCTS & ADMINISTRATION**

### ***10.1 FORMULATIONS***

The active study product will consist of the currently market prescription drug for acne clascoterone cream 1%.

### ***10.2 PRECAUTIONS***

Study products should be used in their intended fashion and not orally consumed or placed in the eyes.

### ***10.3 STUDY PRODUCT ADMINISTRATION***

The subjects will apply the clascoterone cream 1% twice daily.

### ***10.4 PACKAGING, LABELING, DISTRIBUTION***

Study products will be dispensed in the packaging provided by the sponsor.

### ***10.5 STORAGE AND ACCOUNTABILITY OF STUDY PRODUCT***

The study product will be stored at room temperature in a locked, limited access area at the study site. Access to the study product will be limited to the investigator and staff members designated to dispense study medication. A study product log will be used to record the dispensation and return of all study product. The subject number/initials, and the initials and date of the person dispensing and receiving the returned study product will be documented on this form.

### ***10.6 CODE DISCLOSURE***

All subjects will receive the same study product and no code will be maintained.

## 11. ADVERSE EVENTS

### 11.1 ADVERSE REACTIONS PREVIOUSLY REPORTED

The study product has been reported to rarely produce skin irritation.

### 11.2 ADVERSE EXPERIENCES

An adverse experience is defined as any untoward medical occurrence (sign, symptom or laboratory finding), regardless of severity and whether or not attributed to the study product.

The investigator/coordinator will report all adverse experiences (AEs) that occur throughout the study. All AEs will be recorded in the appropriate AE log. The report will include: date of onset, a description of the AE, severity, seriousness, action taken, relationship to the study drug, outcome of the event, and date of resolution.

#### 11.2.1 ASSESSMENT OF SEVERITY

The intensity or severity of an AE is characterized as:

Mild: AE which is easily tolerated.

Moderate: AE sufficiently discomforting to interfere with daily activity.

Severe: AE which prevents normal daily activities.

Subjects who are withdrawn from the study due to any AE will be followed by the investigator until the outcome is determined. The investigator will summarize and document all information relating to the AE and follow up.

#### 11.2.2 RELATIONSHIP TO STUDY PRODUCT

The relationship is characterized as:

Not Related - applies to any adverse experience that is clearly not related to use of the study product.

Possible - means the association of the adverse experience with the study product is unknown; however, a relationship between study product and experience cannot be ruled out.

Probable - there is a reasonable temporal relationship between the use of the study product and the adverse experience. Based upon the investigator's clinical experience, the association of the event with the study product seems likely.

Definite - The AE occurs following the application of the study product and it cannot be reasonably explained by any other known characteristics of the subject's clinical state, environmental or toxic factors, or other modes of therapy administered to the subject. It disappears or decreases upon discontinuation of the study product and reappears on a re-challenge of the study product. This is necessary to evaluate allergic or irritant contact dermatitis.

### **11.3 SERIOUS ADVERSE EVENTS**

Definition: An SAE is defined as any adverse experience occurring that results in any of the following outcomes:

1. death
2. immediately life-threatening illness
3. hospitalization ( > 24 hours) or prolongation of existing hospitalization
4. a persistent or significant disability
5. a congenital anomaly/birth defect
6. “other” important medical event

These are not anticipated, however, should an SAE occur, the primary investigator ( [REDACTED] ) will immediately notify the sponsor.

## **12. STATISTICAL METHODS**

Along with descriptive statistics (means, standard deviations and percentages), investigator and subject ordinal nonparametric data will be analyzed using the Wilcoxon signed rank test. Change will be considered significant at a p value less than or equal to 0.05. [REDACTED]

[REDACTED] sebumeter measurements will be assessed with a Student's t test again with significance at a p value less than or equal to 0.05.

### **12.1 SAMPLE SIZE RATIONALE**

A sample size of 40 study subjects was chosen by the study sponsor.

### **12.2 SIGNIFICANCE LEVEL**

Significance is defined at the  $p < 0.05$  level based on a two-sided test.

### **12.3 DROP-OUT (PRODUCT TOLERABILITY) ASSESSMENT**

Subjects who discontinue will be queried as to any side effects experienced by the study products.

### **12.4 SAFETY ASSESSMENT**

Incidence of all adverse events reported during the study will be summarized. Tabulated summaries will include adverse events grouped by relation to study product.

## **12.5 ENDPOINTS**

### **12.5.1 PRIMARY EFFICACY ENDPOINT**

The primary efficacy endpoint is the reduction in causal sebum measurements from the forehead obtained with a sebumeter during the study.

### **12.5.2 SECONDARY EFFICACY ENDPOINT**

The secondary efficacy endpoint is the changes in the facial microbiome induced by 8, 12, and 52 weeks of clascoterone 1% cream application

[REDACTED]

[REDACTED]

[REDACTED]

### **12.5.6 SAFETY ENDPOINT**

The safety endpoint is the overall incidence of all adverse events reported during the study.

## **13. ETHICS**

### **13.1 INFORMED CONSENT**

The principles of Informed Consent, according to FDA Regulations and ICH step 5 guidelines on GCPs, will be followed.

Subjects must provide written informed consent prior to any study procedures being completed. Each subject's signed informed consent must be kept on file by the Investigator for Regulatory Authorities' inspection at any time. A copy of the signed and dated consent form will be given to the subject.

### **13.2 INSTITUTIONAL REVIEW BOARD (IRB)**

The study will be submitted to an IRB selected by Dermatology Consulting Services for approval to ensure the safety of the human subjects enrolled in the study.

### ***13.3 SUBJECT CONFIDENTIALITY***

All participants are concerned for the individual subject's privacy and, therefore, all subject data will be identified only by a subject identification number and subject initials. However, in compliance with federal guidelines regarding the monitoring of clinical studies and in fulfillment of his/her obligations to the Sponsor, it is required that the Investigator permit the study monitor and/or FDA representative to review that portion of the subject's medical record that is directly related to the study. This shall include all study relevant documentation including subject medical histories to verify eligibility, laboratory test result reports to verify transcription accuracy, admission/discharge summaries for hospital stays occurring while the subject is enrolled in the study, and autopsy reports for deaths occurring during the study.

As part of the required content of informed consent, the subject must be informed that his/her medical chart may be reviewed by the sponsor, the Sponsor's authorized representative, or a representative of the FDA. Should access to the medical record require a separate waiver or authorization, it is the investigator's responsibility to obtain such permission from the subject in writing before the subject is entered into the study.

## **14. DOCUMENTATION**

### ***14.1 SITE DOCUMENTS REQUIRED FOR INITIATION***

Prior to the initiation of the study, the following items must be received:

- a) Sponsor approval of study
- b) Current curriculum vitae of the Principal Investigator
- c) Copy of Principal Investigator's Medical license
- d) A signed copy of the protocol Investigator's Agreement page
- e) Original Non-Disclosure Agreement
- f) Signed Budget Agreement

### ***14.2 STUDY DOCUMENTS SUPPLIED BY THE SPONSOR***

Dermatology Consulting Services will provide all study documents.

### ***14.3 MAINTENANCE AND RETENTION OF RECORDS***

The study will be conducted according to Good Clinical Practices as outlined in ICH step 5 guidelines by the Food and Drug Administration. It is the responsibility of the Investigator to maintain a comprehensive and centralized filing system of all relevant documentation.

Investigators will be instructed to retain all study records required by the sponsor, as well as the regulations, in a secure and safe facility with limited access. Regulations require retention for a period of at least two years after last

marketing approval and notification from the sponsor. These regulatory documents should be retained for a longer period if required by local regulatory requirements.

Archiving of data - Copies of all pertinent records will be retained by the investigator for at least two years following final approval of the drug and/or notification from the sponsor. These records include documents pertaining to the receipt and return of drug supplies, IRB, Informed Consent, as well as final signed case report forms. No documents shall be transferred from the site or destroyed without first notifying the sponsor. The sponsor will archive the data for the lifetime of the product.

#### 14.3.1 CASE REPORT FORMS (CRF)

CRFs for individual subjects will be provided and completed by Dermatology Consulting Services, as appropriate. CRFs must be legible and complete.

A CRF must be completed and signed by the investigator for each subject enrolled, including those removed from the study for any reason. The reason for removal must be noted on the study conclusion CRF by the investigator for each subject. CRFs must be kept current to reflect the subject's status at each phase during the course of the study. Subjects are not to be identified on CRFs by name; appropriately coded identification and the subject's initials must be used. The investigator must keep a separate log of the subject's names and addresses.

The following documents will be maintained by the research site:

1. Subject Screening Log: This log will reflect the reason any subject screened for the study was found to be ineligible.
2. Study Personnel Signature Log: This log will contain all site personnel along with their responsibilities and signatures. This log will be maintained at the site throughout the study.
3. Monitoring Log: This log will contain the date and purpose of all monitoring visits by the Sponsor.
4. Enrollment Log: This log will contain subject initials and start and end dates for all subjects enrolled.
5. Product Inventory / Packing Slip Log: This log will reflect the total amount of study product shipped to the site and received and signed for by the Investigator.
6. Product Accountability Log: This log will reflect the total amount of study product dispensed to and returned by each subject.

#### 14.3.2 MONITORING

The study will be monitored by a Sponsor appointed representative, if desired.

#### **14.4 *PROTOCOL MODIFICATION***

The procedures defined in the protocol and in the CRF will be carefully reviewed to ensure that all parties involved with the study fully understand the protocol. In order to ensure the validity of the data, no deviations from the protocol may be made unless the issue is broad enough to warrant revision of the protocol. Such revisions must be submitted to and have approval in writing from the Sponsor and the IRB prior to implementation.

#### **14.5 *AUDITS/INSPECTIONS***

During the course of the study and/or after it has been completed, one or more site visits may be undertaken by auditors as authorized representatives of the Sponsor.

**APPENDIX I: CASE REPORT FORMS**

The following documents are attached:

1. Screening Questionnaire
2. Inclusion/Exclusion Criteria
- [REDACTED]
5. Sponsor Questionnaire
6. Sebumeter Measurements
7. Adverse Event Assessment
8. Study Termination
9. Informed Consent Form (as a separate file)
10. Subject Diary (as a separate file)

SCREENING QUESTIONNAIRE

DATE\_\_\_\_\_

NAME\_\_\_\_\_

LAST	FIRST	MIDDLE INITIAL
------	-------	----------------

DATE OF BIRTH\_\_\_\_\_ AGE\_\_\_\_\_

SOCIAL SECURITY\_\_\_\_\_-\_\_\_\_\_-\_\_\_\_\_

GENDER AT BIRTH\_\_\_\_\_ RACE\_\_\_\_\_

STREET ADDRESS\_\_\_\_\_

CITY\_\_\_\_\_ STATE\_\_\_\_\_ ZIP\_\_\_\_\_

E-MAIL\_\_\_\_\_

CELL PHONE (     )\_\_\_\_\_ - \_\_\_\_\_ CELL PHONE CARRIER\_\_\_\_\_

EMERGENCY CONTACT  
NAME\_\_\_\_\_ RELATIONSHIP\_\_\_\_\_

EMERGENCY CONTACT  
CELL PHONE (     )\_\_\_\_\_ - \_\_\_\_\_

I understand federal law requires any person who receives more than \$600 in a calendar year from our office must be issued a 1099 tax form. I understand I must provide my social security number for this reason.

SIGNATURE\_\_\_\_\_ DATE\_\_\_\_\_

## INCLUSION/EXCLUSION CRITERIA

### Inclusion Criteria:

1. Males and females 12+ years of age.
2. Subjects with mild to moderate acne.
3. Subjects must possess 10-100 total non-inflammatory lesions (open comedones and closed comedones), 10-50 total inflammatory lesions, no cysts, and up to 2 nodules (if deemed appropriate by the PI) on the face.
4. Subjects with all Fitzpatrick skin types I-VI.
5. Subjects who agree to use only the study products for acne treatment. No other medicated cleansers or moisturizers or acne treatments of any kind are allowed.
6. Subjects agree not to introduce any new colored cosmetics or skin care products while participating in the study (lipsticks, eye shadows, facial foundations, blush, powder, cleansers, moisturizers).
7. Subjects agree to arrive at all visits with a clean face, having washed his/her face and removed all facial and eye makeup products within 2 hours to 4 hours prior to the visit and is not to use/apply any topical facial product(s) until the visit is completed.
8. No known medical conditions that, in the investigator's opinion, may interfere with study participation.
9. Women of childbearing potential must be willing to use a form of birth control during the study. For the purpose of this study, the following are considered acceptable methods of birth control: oral contraceptives, Norplant®, Depo-Provera®, double barrier methods (e.g., condom and spermicide) and abstinence.
10. Subjects are dependable and able to follow directions and willing to comply with the schedule of visits.
11. Subjects in generally good physical and mental health.
12. Able to read, write, speak, and understand English
13. Individual (and/or his/her legally acceptable representative, as applicable) has signed the Consent for Photograph Release and ICD (and/or Assent Document, as applicable) including Health Insurance Portability and Accountability Act (HIPAA) disclosure.
14. Subject must avoid sun exposure, or use sunscreen if sun exposure is unavoidable.
15. Subject must avoid professional or facial spa procedures during the study.

### Exclusion Criteria:

1. Any dermatological disorder, which in the investigator's opinion, may interfere with the accurate evaluation of the subject's skin characteristics, except for the study condition of acne.
2. Subjects who are not willing to use the assigned study product to their face as instructed.
3. Subjects who have acne nodules/cysts representative of severe acne.
4. Subjects who are currently using, planning to use during the study or has used any of the following in the specified time range (based on subject report):
  - a. **1 month prior to Visit 1:** Prescription (oral or topically applied on the face) antibiotics, inhaled steroids (except those prescribed for allergies), or

- hormones (pre- or post-menopausal hormone-replacement therapy; insulin, etc.), or other medications that could make skin more sensitive or have an effect on the skin, as determined by the PI or designee. Oral contraceptives are acceptable.
- b. **1 month prior to Visit 1:** Prescription medication for acne (e.g. doxycycline, minocycline, clindamycin, sulfamethoxazole and trimethoprim [Bactrim], tetracycline, erythromycin, azithromycin, or Vibramycin®)
  - c. **1 month prior to Visit 1:** Topical prescription retinoids (e.g. Retin-A®, Retin-A Micro®, Renova®, Adapalene, Tazarotene, Avita®, Tazorac®, Avage®, Differin®), azelaic acid, benzoyl peroxide, dapsone, sodium sulfacetamide, Epiduo®, or other similar prescription drug on the face
  - d. **6 months prior to Visit 1:** Accutane or other oral retinoid
  - e. **2 weeks prior to Visit 1:** Any of the following on the face:
    - i. Light therapy
    - ii. OTC topical medications/products (including antiacne or antibacterial agents, topical anti-inflammatories, topical retinoids, etc.). Sunscreens (SPF) are acceptable.
- 5. Females who are pregnant, lactating, or planning to become pregnant during the study or within 30 days of study completion. (Subject must document her response in either the source documentation or informed consent/assent forms).
  - 6. Subject has a surgery and/or invasive medical procedure planned during the study.
  - 7. Subject has observable suntan, scars, nevi, tattoo, excessive hair (including beard, mustache, or goatee), or other dermal conditions on the face that could interfere with study evaluations or confound study results, as determined by the PI or designee.
  - 8. Subject is taking medications that would mask an adverse event (AE) or influence the study results, including:
    - a. Immunosuppressive drugs and steroidal and/or non-steroidal anti-inflammatory drugs within 3 months before Visit 1 and during the study.
    - b. Regular use of antihistamines within 1 month before Visit 1 and during the study.
  - 9. Subject has a history of or a concurrent health condition/situation, which in the opinion of the PI, if medically qualified, or Study Physician, may put the individual at significant risk, confound the study results, or interfere significantly with the individual's participation in the study.
  - 10. Subject is an employee/contractor or immediate family member of the PI, Study Site, or Sponsor.
  - 11. Subjects with clinically significant unstable medical disorders.

**Dermatology Consulting Services, PLLC**

**Protocol Number: DCS-67-22**

12. Subjects who are unwilling or unable to comply with the requirements of the protocol.
13. Subjects with any known allergies or sensitivities to the study acne products.
14. Subjects who are currently under the care of a dermatologist for acne.
15. Subjects who are currently experiencing an acne flare.
16. Subjects who have history of a psychological illness or condition that would interfere with their ability to understand and follow the requirements of the study.
17. Subjects having started hormone replacement therapies (HRT) or hormones for birth control less than 3 months prior to the study entry or who plan on starting, stopping or changing doses of HRT or hormones for birth control during the study.

All inclusion criteria must be met and none of the exclusion criteria. Circle any inclusion criteria that are not met and any exclusion criteria that are met and declare the subject a screening failure.

**Dermatology Consulting Services, PLLC**  
**Protocol Number: DCS-67-22**

TIMEPOINT	IGA
Baseline	
Week 2	
Week 4	
Week 6	
Week 8	
Week 10	
Week 12	
Week 16	
Week 20	
Week 24	
Week 28	
Week 32	
Week 36	
Week 40	
Week 44	
Week 48	
Week 52	

TIMEPOINT	PAPULES	PUSTULES	CLOSED COMEDONES	OPEN COMEDONES
Baseline				
Week 2				
Week 4				
Week 6				
Week 8				
Week 10				
Week 12				
Week 16				
Week 20				
Week 24				
Week 28				
Week 32				
Week 36				
Week 40				
Week 44				
Week 48				
Week 52				

**Dermatology Consulting Services, PLLC**  
**Protocol Number: DCS-67-22**

TIMEPOINT	Oily Appearance	Pore Size	Facial Shine
Baseline	0 1 2 3 4	0 1 2 3 4	0 1 2 3 4
Week 2	0 1 2 3 4	0 1 2 3 4	0 1 2 3 4
Week 4	0 1 2 3 4	0 1 2 3 4	0 1 2 3 4
Week 6	0 1 2 3 4	0 1 2 3 4	0 1 2 3 4
Week 8	0 1 2 3 4	0 1 2 3 4	0 1 2 3 4
Week 10	0 1 2 3 4	0 1 2 3 4	0 1 2 3 4
Week 12	0 1 2 3 4	0 1 2 3 4	0 1 2 3 4
Week 16	0 1 2 3 4	0 1 2 3 4	0 1 2 3 4
Week 20	0 1 2 3 4	0 1 2 3 4	0 1 2 3 4
Week 24	0 1 2 3 4	0 1 2 3 4	0 1 2 3 4
Week 28	0 1 2 3 4	0 1 2 3 4	0 1 2 3 4
Week 32	0 1 2 3 4	0 1 2 3 4	0 1 2 3 4
Week 36	0 1 2 3 4	0 1 2 3 4	0 1 2 3 4
Week 40	0 1 2 3 4	0 1 2 3 4	0 1 2 3 4
Week 44	0 1 2 3 4	0 1 2 3 4	0 1 2 3 4
Week 48	0 1 2 3 4	0 1 2 3 4	0 1 2 3 4
Week 52	0 1 2 3 4	0 1 2 3 4	0 1 2 3 4

TIMEPOINT	Peeling	Dryness	Redness	Swelling
Baseline	0 1 2 3 4	0 1 2 3 4	0 1 2 3 4	0 1 2 3 4
Week 2	0 1 2 3 4	0 1 2 3 4	0 1 2 3 4	0 1 2 3 4
Week 4	0 1 2 3 4	0 1 2 3 4	0 1 2 3 4	0 1 2 3 4
Week 6	0 1 2 3 4	0 1 2 3 4	0 1 2 3 4	0 1 2 3 4
Week 8	0 1 2 3 4	0 1 2 3 4	0 1 2 3 4	0 1 2 3 4
Week 10	0 1 2 3 4	0 1 2 3 4	0 1 2 3 4	0 1 2 3 4
Week 12	0 1 2 3 4	0 1 2 3 4	0 1 2 3 4	0 1 2 3 4
Week 16	0 1 2 3 4	0 1 2 3 4	0 1 2 3 4	0 1 2 3 4
Week 20	0 1 2 3 4	0 1 2 3 4	0 1 2 3 4	0 1 2 3 4
Week 24	0 1 2 3 4	0 1 2 3 4	0 1 2 3 4	0 1 2 3 4
Week 28	0 1 2 3 4	0 1 2 3 4	0 1 2 3 4	0 1 2 3 4
Week 32	0 1 2 3 4	0 1 2 3 4	0 1 2 3 4	0 1 2 3 4
Week 36	0 1 2 3 4	0 1 2 3 4	0 1 2 3 4	0 1 2 3 4
Week 40	0 1 2 3 4	0 1 2 3 4	0 1 2 3 4	0 1 2 3 4
Week 44	0 1 2 3 4	0 1 2 3 4	0 1 2 3 4	0 1 2 3 4
Week 48	0 1 2 3 4	0 1 2 3 4	0 1 2 3 4	0 1 2 3 4
Week 52	0 1 2 3 4	0 1 2 3 4	0 1 2 3 4	0 1 2 3 4

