Design:	
Female and male subjects will be enrolled in this single site study to evaluate the effect of clascoterone cream 1.0% on facial sebum production and acne. Subjects who sign consent and meet all inclusion criteria and none of the exclusion criteria will be enrolled at the baseline visit. Subjects will use their own approved skin care products unchanged for the duration of the study.
 
At baseline visit, subjects will receive the study product. The dermatologist investigator will assess facial appearance in terms of oily appearance, pore size, and facial shine. In addition, she will perform a global acne assessment (IGA), inflammatory lesion counts (papules, pustules) and non-inflammatory lesion counts (open comedones, closed comedones). The dermatologist investigator will assess the tolerability criteria of peeling, dryness, redness, and swelling on a 5-point ordinal scale (0=none, 1=minimal, 2=mild, 3=moderate, 4=severe). Three casual sebumeter measurements will be taken from the central forehead 2-4 hours after the subjects washed prior to presenting to the research center.
 
Subjects will assess the performance of their acne treatment regimen by completing a consumer self-assessment/treatment perception questionnaire provided by the sponsor and a tolerability assessment in terms of stinging, itching, and burning. All tolerability assessments will be made on a 5-point ordinal scale (0=none, 1=minimal, 2=mild, 3=moderate, 4=severe) at each visit. Subjects will be given their diaries and study products and asked to return to the research center in 2 weeks. A reminder text will be sent to

	
encourage compliance prior to the week 2 visit.
 
Subjects will return to the research center at Week 2, Week 4, Week 6, Week 8, Week 10, Week 12, Week 16, Week 20, Week 24, Week 28, Week 32, Week 36, Week 40, Week 44, Week 48, Week 52 for the same assessments. Old study product and diaries will be collected and new diaries and study product dispensed as needed. All the same assessments will be performed as at baseline for all visits. Subjects will continue participation for 52 weeks, at which time their study participation will be completed.
 
Microbiome swabbing for analysis by [REDACTED] will be obtained from all 40 subjects at baseline, week 8, week 12, and week 52.
 
(There is an allowance for an unscheduled visit at any time, if necessary.)

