### 7.2 STUDY CONDUCT PROCEDURES

#### 7.2.1 BASELINE

Female and male subjects will be enrolled in this single site study to evaluate the effect of clascoterone cream [REDACTED] on facial sebum production and acne. Subjects who sign consent and meet all inclusion criteria and none of the exclusion criteria will be enrolled at the baseline visit. Subjects will use their own approved skin care products unchanged for the duration of the study.

At baseline visit, subjects will receive the study product. The dermatologist investigator will assess facial appearance in terms of oily appearance, pore size, and facial shine. [REDACTED]

[REDACTED]  
[REDACTED]  
[REDACTED]  
[REDACTED] Three casual sebumeter measurements will be taken from the central forehead 2-4 hours

after the subjects washed prior to presenting to the research center. A microbiome sample will be taken from the cheek.

[REDACTED]

7.2.2 WEEK 2, WEEK 4, WEEK 6, WEEK 8, WEEK 10, WEEK 12, WEEK 16, WEEK 20, WEEK 24, WEEK 28, WEEK 32, WEEK 36, WEEK 40, WEEK 44, WEEK 48, WEEK 52

Subjects will return to the research center at Week 2, Week 4, Week 6, Week 8, Week 10, Week 12, Week 16, Week 20, Week 24, Week 28, Week 32, Week 36, Week 40, Week 44, Week 48, Week 52 for the same assessments as performed at baseline. Old study product and diaries will be collected and new diaries and study product dispensed as needed at each visit. Subjects will continue participation for 52 weeks, at which time their study participation will be completed.

Microbiome sampling will occur at weeks 8, 12, and 52.

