**Dermatology Consulting Services, PLLC**  
**Protocol Number: DCS-67-22**

TIMEPOINT	Stinging	Burning	Itching
Baseline	0 1 2 3 4	0 1 2 3 4	0 1 2 3 4
Week 2	0 1 2 3 4	0 1 2 3 4	0 1 2 3 4
Week 4	0 1 2 3 4	0 1 2 3 4	0 1 2 3 4
Week 6	0 1 2 3 4	0 1 2 3 4	0 1 2 3 4
Week 8	0 1 2 3 4	0 1 2 3 4	0 1 2 3 4
Week 10	0 1 2 3 4	0 1 2 3 4	0 1 2 3 4
Week 12	0 1 2 3 4	0 1 2 3 4	0 1 2 3 4
Week 16	0 1 2 3 4	0 1 2 3 4	0 1 2 3 4
Week 20	0 1 2 3 4	0 1 2 3 4	0 1 2 3 4
Week 24	0 1 2 3 4	0 1 2 3 4	0 1 2 3 4
Week 28	0 1 2 3 4	0 1 2 3 4	0 1 2 3 4
Week 32	0 1 2 3 4	0 1 2 3 4	0 1 2 3 4
Week 36	0 1 2 3 4	0 1 2 3 4	0 1 2 3 4
Week 40	0 1 2 3 4	0 1 2 3 4	0 1 2 3 4
Week 44	0 1 2 3 4	0 1 2 3 4	0 1 2 3 4
Week 48	0 1 2 3 4	0 1 2 3 4	0 1 2 3 4
Week 52	0 1 2 3 4	0 1 2 3 4	0 1 2 3 4

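### The Appendix I rating forms run from Baseline to Week 52 in one table and no visible text withholds earlier scores, so the layout allows an open-label rater to see them

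*Combined protocol and SAP*

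**What the plan says.** Section 10.6 makes the study open and single-arm: "All subjects will receive the same study product and no code will be maintained". The rater is named in the Synopsis (Design): "The dermatologist investigator will assess facial appearance in terms of oily appearance, pore size, and facial shine". The same investigator also gives the IGA, the lesion counts and the tolerability signs. Under Section 7.2.2, subjects come back at 16 visits "for the same assessments as performed at baseline".

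The forms attached in Appendix I are running tables, each with 17 rows from Baseline to Week 52:

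- IGA, in one table.
- Lesion counts: "TIMEPOINT PAPULES PUSTULES CLOSED COMEDONES OPEN COMEDONES".
- Facial appearance: "TIMEPOINT Oily Appearance Pore Size Facial Shine".
- Investigator tolerability: "TIMEPOINT Peeling Dryness Redness Swelling".
- Subject tolerability: "TIMEPOINT Stinging Burning Itching".

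The appearance and tolerability cells are circled on a 0 to 4 scale; the last row of the appearance table reads "Week 52 0 1 2 3 4 0 1 2 3 4 0 1 2 3 4". Section 14.3.1 asks that case report forms be kept up to date through the study, which fits a running record. Section 12 assigns ordinal investigator and subject ratings to the Wilcoxon signed rank test at 0.05, and Section 12.2 makes the test two-sided. No visible text provides a separate page per visit, masks earlier scores or arranges an independent reading.

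**The concern.** Each visit's rating should be a fresh reading of the face on that day. On a running table, the Week 12 score goes directly beneath Baseline and the scores for Weeks 2 to 10. A rater who already knows the product and the visit can then also see the score to compare against.

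Two effects are possible. Oily appearance, pore size, shine and IGA may drift in the expected direction; the Introduction says the product is believed to work by lowering sebum, so that direction is known to the rater. Irritation scores may instead settle on a column of earlier zeros. The second effect bears on the tolerability endpoint, which the Synopsis defines as investigator-assessed absence of skin irritation at any time.

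With no control arm, nothing cancels a shared drift, and a within-subject test on change counts it as a product effect. Knowledge of the product cannot be removed in this design, but sight of the earlier score can.

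**Working it through.** The plan gives no power, effect size or standard deviation (Section 12.1 says the sponsor chose 40), so there is no figure of its own to reproduce. The check has three steps.

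**1. Which ratings are exposed, and to what.** There are 17 visits, of which 16 are after baseline.

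- Appearance scales and IGA: (3 + 1) x 16 = 64 ratings per subject. False improvement is the worry here.
- Irritation scores: (4 investigator + 3 subject) x 16 = 112. The worry is under-detection; a score of 0 cannot go lower.
- Lesion counts: 4 x 16 = 64. These are counts, and the Synopsis sends them to a t test, so the signed rank illustration below does not apply to them.

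**2. Smallest shift that reaches significance with no opposing changes.** Take 40 subjects, with k rated one grade better and the rest unchanged. All non-zero differences tie in size, so the exact signed rank test reduces to a sign test:

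exact two-sided p = 2 x (1/2)^k

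- k = 5: 2/32 = 0.0625
- k = 6: 2/64 = 0.031

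So 6 of 40 (15%) are needed. The tie-corrected normal approximation without continuity correction has z = k/sqrt(k) = sqrt(k). It gives p = 0.0455 at k = 4 and 0.025 at k = 5. The plan does not say which version would be used.

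**3. The same with opposing changes.** Suppose c subjects move one grade each way by chance, and m others are rated one grade better. Then n = 2c + m, and exact p = 2 x P(Bin(n, 1/2) >= c + m). The documents give no figure for c, so these values are assumptions:

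| c each way | Smallest m, exact test | p | m as share of 40 |
|---|---|---|---|
| 0 | 6 | 0.031 | 15% |
| 2 | 8 | 0.039 | 20% |
| 5 | 10 | 0.041 | 25% |
| 10 | 13 | 0.035 | 32.5% |

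The normal approximation, z = m/sqrt(n), needs 9 at c = 5 (p = 0.039) and 11 at c = 10 (p = 0.048).

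These are properties of the test. They show how many shifted ratings would matter, and do not show how many the form would cause.

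**The case against.** The strongest reply is that open-label knowledge does most of the harm. The investigator knows the product and the visit and sees the same face up to 17 times. The p-values above would be identical if every nudge came from expectation on separate pages. This stands: nothing in the documents separates the form's share from the rest. It does not defend the layout, because sight of the earlier score is the part that can be removed.

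Second, a reader might infer that the investigator does see every earlier score. The documents do not say so. Section 14.3.1 does not say that ratings are made with the running table open, and a visit-level source record is not ruled out. The stinging, burning and itching form does not state who fills it in. Two items in the Appendix I list and most of Section 8.1 are redacted and could hold rating instructions. The supported statement is that the layout allows it and nothing visible prevents it.

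Third, anchoring works both ways. A rater who repeats the last score understates change, which is conservative for the appearance scales, and some would defend access to earlier scores for consistency over 52 weeks. The direction of bias is therefore plausible and not shown. For irritation scores, however, repeating an earlier zero is itself the harm.

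Fourth, the sebumeter form has the same layout, and a reader might extend the point to it. That form records an instrument reading, and the documents give no ground for treating it as a judgement that drifts.

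**Conclusion.** The point holds in limited form. The layout of the IGA, lesion count, appearance and tolerability forms leaves earlier scores open to the rater in a single-arm, open-label study, and this exposure is avoidable. It concerns mainly 64 appearance and IGA ratings per subject, where drift could pass for improvement, and the irritation scores, where anchoring could hide a reaction. The primary sebumeter endpoint (Section 12.5.1) and the secondary microbiome endpoint (Section 12.5.2) are not affected. The rank of the appearance scales may lie in redacted text, and the point does not depend on it.

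A reader might infer that a handful of nudges caused by the form would produce a significant result. That goes too far. The figure of 6 of 40 assumes 34 exact ties and no subject moving the other way; with an assumed 5 to 10 subjects moving each way, 10 to 13 are needed. A reader might also count all 240 post-baseline entries (64 + 112 + 64) as open to false improvement; only the first 64 fit that argument.

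**What to change.** Replace the running tables in Appendix I for IGA, lesion counts, appearance, investigator tolerability, and stinging, burning and itching with one page per visit. Leave the sebumeter form as it is. Add a sentence to Section 7.2.2: each visit's ratings are entered before earlier scores are consulted, and earlier pages are available afterwards for adverse event review.

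The cost is reformatted forms, one sentence, and a small handling step at each visit to keep earlier pages aside until the ratings are entered. No visit, procedure or sample size changes. The downside is that entry errors are less visible at a glance and must be caught by data review. The change works only forward in time: if ratings have already been collected on the running tables, they cannot be repaired, and the limitation should be stated when they are reported.
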